11.4 Serious Adverse Event (SAE) reporting in ECAL trial

All adverse events which meet the definition of serious must be recorded in the participant medical notes, including the causality and severity. The reporting period for SAEs will be from randomisation until 26 weeks after agreed set target quit day/ default target quit day. When an SAE is identified during a scheduled telephone call with a participant, the trial team will notify the research site to investigate.

For all SAEs, the PI or delegate must do one of the following:

1. **Record safety reporting-exempt SAEs** in the medical notes but **not report** them to the trials office on an SAE form as per Section 11.4.1 Serious Adverse Events not requiring reporting to the Trial Office.
2. **Report SAEs to the trial office in a non-expedited manner.** This can only be done for the pre-defined subset of SAEs as per Section 11.4.2 Serious Adverse Events requiring non-expedited reporting to the Trial Office.
3. **Report SAEs to the trial office in an expedited manner** (within 24 hours of the site research team becoming aware of the event). All SAEs not covered by the above 2 categories must be reported as per Section 11.4.3 SAE Reporting process.

Note: when an SAE occurs at the same site at which the participant is receiving a trial product or is being followed up for trial purposes, processes must be in place to make the trial team at the site aware of any SAEs, regardless of which department first becomes aware of the event, in an expedited manner.

In addition, any SAE reported to the trial team by the participant will be passed to the PI to ensure the SAE is noted in the participant's medical notes. Where the SAE requires causality assessment, we will follow up with the PI until resolution of the SAE.

11.4.1 *Serious Adverse Events not requiring reporting to the Trial Office*

Safety reporting exempt SAEs must be recorded in the participant medical notes, including the causality and severity, but for trial purposes these events do not require reporting on the SAE CRF. The following will be considered as safety reporting exempt SAEs:

1. Pre-planned elective hospitalisation for any reason
2. Congenital anomalies or birth defects in the offspring of participants

11.4.2 *Serious Adverse Events requiring non-expedited reporting to the Trial Office*

The population enrolling in ECAL are expected to be admitted for reasons related to COPD. In this case such an SAE is protocol-defined as "expected" (see Section 11.5.2 Assessment of expectedness of an SAE by the CI). The following will be considered as expected SAEs:

1. Admission for exacerbation of COPD
2. Community acquired pneumonia
3. Lung cancer events
4. Cardiovascular events

Such events should still be recorded by the trial team in the participant's medical notes and reported to the Trial Office on the trial outcome CRF, but it does not require expedited reporting (immediately on the site becoming aware of the event) since the assessment of expectedness for

the specified events has been pre-defined. They should be reported within 2 weeks of site being aware of the event.

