1.2 Previous literature

ECs for smoking cessation There are a number of systematic reviews assessing the effectiveness of ECs for smoking cessation, one of which is a Cochrane review.¹⁶ The latest version of the Cochrane review found that nicotine ECs are more effective than nicotine replacement therapy (NRT) (Relative Risk (RR) 1.63, 95% Confidence Interval 1.30 to 2.04) for smoking cessation. These estimates were based on data from six trials.¹⁶ Reviews acknowledge the need for additional high-quality studies testing ECs for smoking cessation against standard treatment (such as NRT), and no EC trials so far have been conducted in patients with COPD.

Effect of vaping on the lungs A number of systematic reviews¹⁷⁻²¹ and reports commissioned by Public Health England/Office for Health Improvement and Disparities have reviewed the evidence on the effect of ECs on health.^{13, 22, 23} However, to date, there are only a limited number of studies that have reported on the effect of EC use on clinical/physiological/cellular lung health outcomes in humans, see below.²⁴⁻²⁶

Clinical measures of lung health - respiratory symptoms, exacerbations and infections

Smoking increases the risk of chronic respiratory symptoms, and there is a decrease in symptoms in patients with COPD after smoking cessation.²⁷ Improvements in symptoms in quitters compared to continuing smokers have been reported in secondary analyses from smoking

cessation trials in COPD patients,²⁸ including The Lung Health Study.²⁷ Etter et al. demonstrated that cough, wheeze, breathlessness when climbing stairs, and sputum production improve rapidly after one month of smoking cessation in an internet sample of 252 COPD patients who quit smoking.²⁹

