1.3.3 Justification for design

To definitively test the effectiveness and cost-effectiveness of EC for smoking cessation compared with NRT in COPD patients, a randomised controlled trial (RCT) is required with embedded economic analysis.

To investigate the effect of switching to vaping on lung health and wellbeing, a cohort analysis is necessary. For the cohort analysis, participants will be re-grouped based on their smoking and vaping status throughout the trial into vapers, quitters or smokers, rather than being analysed by trial arm. This is necessary as many people in each arm of the trial will relapse back to smoking, and therefore analysis by trial arm will not show the effect of vaping, quitting or smoking on lung health/wellbeing as trial arms will contain a mixture of these.

1.3.4 *Justification for choice of intervention*

We will be using a modern EC starter pack which will include an initial supply of e-liquid. There is no recommended length of use of ECs for smoking cessation as is the case for NRT where up to 12 weeks is recommended. Participants will therefore be given an initial supply of a sufficient amount to start using the EC (up to 20 mg nicotine/ml) and then advised to source continuing supplies. Participants will be advised how to continue sourcing supplies according to preference which may include changing devices, flavours and strengths as needed. This strategy was used successfully in our previous trials.^{30 55}

ECs will be compared with up to 12 weeks supply of combination NRT. Participants will be encouraged to use a nicotine patch in combination with a fast-acting product (e.g. gum, lozenge, microtab) as this has been shown to be the most effective way of using NRT⁵⁶ and is recommended by NICE.⁵⁴ Taking a pragmatic approach, should participants indicate they are not able to use the patch (e.g. due to previous reactions to nicotine patch), they will be able to choose two fast-acting products. Choice of fast-acting nicotine product for all participants will also be dependent on product availability.

1.3.5 *Justification of choice of primary outcome*

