3. TRIAL DESIGN AND SETTING

3.1 Trial design

The effectiveness and cost-effectiveness of ECs will be tested by conducting a national, multicentre, phase III, two arm RCT with internal pilot and economic evaluation. A target of 1250 participants will be recruited and randomised in a 1:1 ratio to either:

- Intervention (EC): EC Starter kit and initial supply of e-liquid; or
- Comparator (NRT): Up to 12 weeks of combination NRT (e.g., patch + oral product)

The trial includes two nested cohort studies assessing lung health and wellbeing.

The trial follow-up time points (and therefore outcome measures) will be established based on the TQD. If participants are unable to be contacted to set a TQD then a default TQD will be set (approximately 2 weeks after the baseline visit) for follow up time points to be based on. Participants will be followed up for 52 weeks post TQD.

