8. TRIAL INTERVENTION

8.1 Trial interventions and dosing schedule

Intervention arm: Electronic Cigarettes (EC) - Participants will receive an EC starter pack and an initial supply of e-liquid to start using the e-cigarette (up to 20 mg nicotine/ml). Participants will be advised on how to continue sourcing further supplies themselves from reputable vendors in their preferred nicotine strength and flavours. Participants in the intervention arm will be offered weekly telephone behavioural support up to 4 weeks post quit.

Comparator arm: Combination Nicotine Replacement Therapy (NRT) - Participants will receive up to 12-week supply of a nicotine patch plus a fast-acting nicotine product to be used in combination. A pragmatic approach to product allocation will allow for variation based on participant preference and availability. Participants who do not wish to use patches (e.g. due to previous experience of skin irritation) will be offered two types of fast acting product. Participants in the comparator arm will also be offered weekly telephone behavioural support up to 4 weeks post quit.

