11.3 Adverse event reporting in the ECAL trial

The reporting period for AEs will be from randomisation until 26 weeks after agreed target quit day/ default target quit day. By this time point the trial supply of intervention product will have ended.

The safety profile for this trial population and interventions are well characterised so although the severity and causality of all AEs should be recorded in the patient's medical notes, a strategy of targeted reporting (to the sponsor) of AEs will not affect the safety of participants. Only the following AEs will be reported via the CRF completed during the scheduled follow up appointments and behavioural support calls:

- Rash/local skin irritation
- Nausea/vomiting
- Throat/mouth irritation
- Sleep disturbances
- Dizziness
- Headache
- Constipation

- Diarrhoea

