11.5.2 Assessment of expectedness of an SAE by the CI

On receipt of an SAE CRF, the Trial Office will forward it, with the unique reference number, to the Chief Investigator (CI) or delegate(s) who will independently* review the causality of the SAE. An SAE judged by the PI or CI or delegate(s) to have a reasonable causal relationship (“Related” as per Table 5: Categories of causality) with the intervention will be regarded as a related SAE (i.e., SAR). The severity and causality assessment given by the PI will not be downgraded by the CI or delegate(s). If the CI or delegate(s) disagrees with the PI’s causality assessment, the opinion of both parties will be documented, and where the event requires further reporting, the opinion will be provided with the report.

*Where the CI is also the reporting PI an independent clinical causality review will be performed.

The CI or delegate(s) will also assess all related SAEs for expectedness with reference to the criteria in table 6.

Table 6: Categories of expectedness

Category	Definition
Expected	An adverse event that is consistent with known information about the trial related procedures or that is clearly defined in the reference safety information (RSI).
Unexpected	An adverse event that is not consistent with known information about the trial related procedures and/or is not clearly defined in the RSI.

The most recently published Summary of Product Characteristics (SmPC) found on the Electronic Medicines Compendium (emc) for 25mg Transdermal Patches with reference to *Section 4.8 Undesirable effects* will be used for the purposes of the RSI. This is reflective of all NRTs. E-Cigarettes are a commercial product not a medical product. As such there is no requirement for safety profiling and no SmPC to inform the RSI. The most recently published SmPC for 15mg Inhalator will be used as a guide on which to base assessment of expectedness (as per MHRA guidance ref: [Guidance for licensing electronic cigarettes and other inhaled nicotine-containing products as medicines - GOV.UK \(www.gov.uk\)](https://www.gov.uk/guidance/guidance-for-licensing-electronic-cigarettes-and-other-inhaled-nicotine-containing-products-as-medicines)).

The CI will undertake review of all SAEs and may request further information from the clinical team at site for any given event(s) to assist in this.

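### Section 11.4.2 labels four SAE classes expected and keeps them off the form that starts causality and SUSAR review; the 26-week end of SAE reporting rests on a reason that does not fit the e-cigarette arm

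*Protocol*

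**What the plan says.** **Routing and expectedness.** Section 11.4.2 names four kinds of SAE likely in people with COPD: admission for an exacerbation, community acquired pneumonia, lung cancer events, and cardiovascular events without restriction. It introduces them with "The following will be considered as expected SAEs", refers to section 11.5.2 for that label, and has sites report them on a trial outcome CRF within 2 weeks. Section 11.4.3 keeps the SAE CRF, due within 24 hours, for SAEs listed in neither 11.4.1 nor 11.4.2.

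Section 11.5.1 asks the PI for a causality category on the SAE CRF. In section 11.5.2 the CI's independent causality review begins when the Trial Office receives that form. The section continues: "The CI or delegate(s) will also assess all related SAEs for expectedness with reference to the criteria in table 6". Table 6 ties expectedness to the reference safety information (RSI) or to what is known about trial procedures. Further on, the same section says the CI reviews all SAEs.

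**Reporting window.** Section 11.4 states: "The reporting period for SAEs will be from randomisation until 26 weeks after agreed set target quit day/ default target quit day". It gives no reason of its own. The reason stands in section 11.3, for AEs over the same window: "By this time point the trial supply of intervention product will have ended". Follow-up is longer. Section 3.1 says "Participants will be followed up for 52 weeks post TQD". For the e-cigarette arm, section 1.3.4 notes that "There is no recommended length of use of ECs for smoking cessation", section 8.1 says "Participants will be advised on how to continue sourcing further supplies themselves from reputable vendors", and section 9.2.2 measures continued use of the allocated product at 52 weeks.

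**The concern.** The word expected carries two meanings. In 11.4.2 it means common in people with this disease. In 11.5.2 it means listed in the RSI or known from trial procedures. Only the second meaning serves to decide whether a related SAE is a SUSAR, yet 11.4.2 says expectedness for its four classes is already settled.

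The form a site fills in also decides what follows. Independent causality review, the expectedness check and the SUSAR clocks in section 11.6 are all written as following from the SAE CRF. The four classes are kept off that form, and they include cardiac and respiratory events for which a link to nicotine or an inhaled product would naturally be asked about. The protocol itself treats the question as open: section 1.2 says "no EC trials so far have been conducted in patients with COPD", and section 1.1 refers to unanswered questions about health effects in this group.

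The reporting window is a separate, secondary matter. Its stated reason assumes that exposure ends with trial supply. In the e-cigarette arm the trial supplies only a starter amount, and continued self-sourced use is part of the strategy.

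**Working it through.** The protocol gives no SAE rate and no figure for this point to reproduce, and the sample size does not depend on it. The check is a comparison of passages plus short arithmetic.

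**1. The two routes side by side**

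| Step | SAE CRF route (11.4.3, 11.5) | Four classes (11.4.2) |
|---|---|---|
| Deadline to Trial Office | 24 hours | 2 weeks |
| PI causality sent to the trial | yes (11.5.1) | none stated; medical notes only (11.4) |
| Independent CI causality review | on receipt of the form (11.5.2) | no route stated; 11.5.2 mentions all SAEs |
| Basis for expectedness | RSI or trial procedures (Table 6) | pre-defined from the population's disease |
| Exception for related or fatal events | not needed | none stated |

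**2. One event traced through.** Take, as a hypothetical, a cardiovascular admission at week 10 in an e-cigarette participant that the PI judges possibly related.
- Under 11.5.1 and 11.5.2, possibly counts as related, so the event is a serious adverse reaction. Expectedness is then checked against the reference document, which for e-cigarettes is the inhalator SmPC used as a guide. If the event is not there, it is a SUSAR.
- Under 11.4.2 the same event goes on the outcome CRF and already counts as expected.

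The outcome depends on which section is followed. The RSI content is not in the protocol, so it cannot be checked whether a given event is listed there. The conflict lies in the basis for the judgement.

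**3. Timing, if such an event is later recognised as a SUSAR.** Section 11.6 counts 7 days (fatal or life-threatening) or 15 days (other) from notification. Assuming that means receipt by the Trial Office, the longest time from site awareness is:
- SAE CRF: 1 + 7 = 8 days, or 1 + 15 = 16 days
- outcome CRF: 14 + 7 = 21 days, or 14 + 15 = 29 days

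**4. Reporting window**
- Post-TQD weeks without SAE reporting: 52 − 26 = 26, and 26/52 = 50%.
- From randomisation, with TQD about 2 weeks after baseline (8.1.1): 26/(2 + 52) = 26/54 = 48%.
- E-cigarette arm, 625 participants: 625 × 0.5 = 312.5 person-years at most. With the 3% loss of section 15.1: 625 × 0.97 × 0.5 = 303.
- Illustration only, as no rate is given: at 1%, 2% or 5% per person-year, 312.5 × rate = about 3, 6 or 16 events in that arm outside the window.

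**5. What is still captured to week 52.** Exacerbations, upper respiratory infections, CAT and CCQ symptoms and spirometry (9.2.2); COPD-related admissions and emergency visits (16.2); and deaths during participation (10.11). Without a stated safety route after week 26 are chiefly non-fatal cardiovascular events, pneumonia and lung cancer.

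**The case against.** Much can be said for the plan.

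- **Causality is not ignored.** Section 11.4 requires causality and severity in the medical notes for every SAE, and says the trial team will follow up with the PI where causality assessment is needed. Section 11.5.2 says the CI reviews all SAEs. A reader might infer that these events go unassessed or could never become SUSARs, but the text does not support that. What stands is that no form or step carries the four classes and their causality to the CI, and that the expected label conflicts with Table 6.
- **The events do reach the Trial Office**, within 2 weeks, up to week 26. The DMC may review any SAE (11.6) and receives safety data (18.6). A reader might infer that harm would be understated to the DMC; this is not shown.
- **The second half of follow-up is not blind**, as step 5 of the working shows. A randomised comparison can reveal an excess of captured events without a causality judgement. This narrows the gap but does not close it.
- **The window is deliberate.** The e-cigarette is not an IMP (8.5.1), and Table 4 defines adverse reactions against the IMP. Even so, 11.5.2 sets an expectedness reference for e-cigarettes and 10.11 refers to SAEs and SUSARs related to them, so the protocol means to assess them. Section 1.3.3 expects many in each arm to relapse to smoking, so 312.5 person-years is an upper limit on exposure.
- **The targeted AE list.** A reader might fault it for having little that is respiratory. CAT and CCQ already measure COPD symptoms to week 52, so adding such items would largely duplicate a secondary outcome.

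**Conclusion.** The main point holds as an internal contradiction. Section 11.4.2 settles expectedness from the underlying disease and uses a form outside the review process; section 11.5.2 settles it from the RSI or trial procedures and starts review from the SAE CRF. The general statement that the CI reviews all SAEs does not resolve this, because no route is given. A related event in the four classes could be missed as a SUSAR, or recognised up to 13 days later (14 − 1) than through the SAE CRF. The passages must be reconciled.

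The secondary point also holds: the stated reason for stopping at 26 weeks suits up to 12 weeks of NRT but not continued self-sourced e-cigarette use. The gap is 50% of post-TQD follow-up, limited chiefly to the event types named in step 5.

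The number of events affected is unknown, because the protocol gives no SAE rate. A reader might suppose that the four classes make up most serious events in COPD; no figure in the document supports or refutes that. The timing figures assume that sites use the full periods allowed.

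**What to change.** **Section 11.4.2 (main change).** Remove the population-based expected label and call these anticipated, non-expedited events. Add the PI's causality category to the outcome CRF. Keep the 2-week route only for events judged unrelated, and send any judged related through the SAE CRF. State that expectedness is decided under section 11.5.2 alone, and say there how outcome-CRF events reach the CI's review. Cost: one protocol amendment, one CRF field, site guidance, and an SAE form for each related event. Unrelated events keep the light route.

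**Sections 11.3 and 11.4 (secondary change).** Extend SAE reporting in both arms to the 52-week assessment, so that the comparison stays symmetric. At the least, record serious cardiovascular, pneumonia and lung cancer events by arm at the 52-week visit, which already takes place. The full extension brings more SAE forms, with 24-hour reporting for those outside the listed classes, and more CI review between weeks 26 and 52. The smaller option costs a few fields, but without causality review. If the 26-week limit is kept, give a reason that applies to the e-cigarette arm.

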10.11 Withdrawal and changes in level of participation

Participants will be able to withdraw from the trial at any time. This will not put at risk their usual medical care for COPD. Failure to be contacted as part of the trial will not count as withdrawal from the trial. The only trial withdrawals will be the following:

- **No behavioural support calls:** The participant would no longer like to receive the behavioural support calls but is willing to be followed up in accordance with the schedule of assessments (i.e., the participant has agreed that data can continue to be collected and used in the trial analysis).
- **No further data collection:** The participant is not willing to be followed up in any way for the purposes of the trial AND does not wish for any further data to be collected (i.e., only data collected prior to any changes of levels in participation can be used in the trial analysis).

Participants are free to stop using the allocated intervention (ECs or NRT) at any time; the participant will not be withdrawn in these circumstance. In the event of a Serious Adverse Event (SAE) or Suspect Unexpected Serious Adverse Reaction (SUSAR) that is judged to be related to NRT or EC, the Chief Investigator (CI) will review the case and if deemed appropriate, the participant will be advised to stop using the medication.

The details of withdrawal should be clearly documented in a withdrawal form. Participants will be asked their reason for withdrawal, but it will be made clear that they are not obliged to give a reason.

In any case of withdrawal, participants will be offered standard care for smoking cessation as per local site protocol for COPD. Additionally, if a participant dies or is lost to follow-up during their participation in the trial, this should also be documented in the source documents and the trial team at BCTU should be notified.

The Trial Office will inform the research sites and QMUL if they are informed by a participant that they wish to withdraw from the trial and vice versa.

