11.4.3 Serious Adverse Events requiring expedited reporting to the Trial Office

All SAEs not listed in section 11.4.1 or section 11.4.2 must be reported to the Trial Office on a trial specific SAE CRF within 24 hours of the site research team becoming aware of the event.

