If the event is unexpected (i.e., it is not defined in the approved version of the RSI) it will be classified as a Suspected Unexpected Serious Adverse Reaction (SUSAR).

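### Section 11.4.2 pre-defines four classes of SAE as expected and keeps them off the SAE form, in conflict with section 11.5.2, so a related event in these classes has no stated route to causality review by the chief investigator or to SUSAR classification

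*Protocol*

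**What the plan says.** Section 11.4 requires causality and severity to be written in the medical notes for every SAE. It then tells the PI to use one of three routes: no report, non-expedited report, or expedited report.

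- **Section 11.4.2 (non-expedited).** The stated reason is that this population is likely to be admitted because of COPD. "The following will be considered as expected SAEs": admission for COPD exacerbation, community acquired pneumonia, lung cancer events and cardiovascular events. These are to be "reported to the Trial Office on the trial outcome CRF, but it does not require expedited reporting", on the ground that their expectedness has been settled in advance. On timing: "They should be reported within 2 weeks of site being aware of the event". No exception is made for related, fatal or unusually severe cases. The section cites 11.5.2 as the place where expectedness is dealt with.
- **Section 11.4.3 (expedited).** The limit here is 24 hours: "All SAEs not listed in section 11.4.1 or section 11.4.2 must be reported to the Trial Office on a trial specific SAE CRF".
- **Section 11.5.1.** The PI grades causality (Table 5) when completing the SAE form.
- **Section 11.5.2.** "On receipt of an SAE CRF, the Trial Office will forward it" to the CI, who reviews causality independently. "The CI or delegate(s) will also assess all related SAEs for expectedness with reference to the criteria in table 6". Table 6 counts an event as expected if it fits what is known about the trial procedures or is clearly defined in the RSI. The section also says that the CI reviews all SAEs. Finally: "If the event is unexpected (i.e., it is not defined in the approved version of the RSI) it will be classified as" a SUSAR.
- **Table 4 (section 11.1).** A SUSAR is a serious adverse reaction whose nature or severity does not fit the product information.
- **Section 10.11.** Where an SAE has a judged link with either product, "the Chief Investigator (CI) will review the case and if deemed appropriate, the participant will be advised to stop using the medication".

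**The concern.** Two things do not fit together.

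First, there are two rules for expectedness. Section 11.4.2 decides it by diagnosis, for whole classes, because of the underlying disease. Section 11.5.2 and Table 4 decide it by comparing the individual related event with the RSI or product information. Section 11.4.2 points to 11.5.2 for support, but 11.5.2 contains no such list. The stated reason, COPD-related admission, also does not explain why cardiovascular and lung cancer events appear without any qualifier.

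Second, the review procedure is tied to a form that the listed events do not use. A site that follows 11.4.2 to the letter sends an outcome form, and nothing then says how the PI's view on relatedness reaches the Trial Office or the CI.

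At stake is whether related serious respiratory and cardiovascular events, in COPD patients given nicotine or an inhaled product, are recognised as reactions and reported in time. SUSAR reports and the annual safety report (section 11.6) can include only what the Trial Office knows to be related.

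**Working it through.** No sample-size, power or event figure is involved. The check is to trace one event through the text and then add the stated reporting times.

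**Test case:** a cardiovascular SAE that the PI considers possibly related and that is not defined in the RSI.

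| Step | Read from 11.4.2 and 11.4.3 | Read from 11.5.2 and Table 4 |
|---|---|---|
| Expected? | Yes, by membership of the list | No, because it is not in the RSI |
| Form | Trial outcome CRF | SAE CRF starts the procedure |
| Time to Trial Office | 2 weeks | 24 hours (11.4.3, 11.5) |
| PI causality grading on a form | None stated | Done when the SAE CRF is completed (11.5.1) |
| Independent CI causality review | No trigger stated | Triggered by receipt of the SAE CRF |
| Classification | Expected, so not a SUSAR | SUSAR |

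1. Section 11.4 makes the routes alternatives, and 11.4.3 limits the SAE CRF to events outside 11.4.1 and 11.4.2. The test case therefore gets no SAE CRF.
2. Sections 11.5.1 and 11.5.2 start form-based PI grading, forwarding and independent CI causality review from an SAE CRF. For the test case none of these is triggered.
3. Section 11.5.2 also says that the CI reviews all SAEs and assesses every related SAE for expectedness. On that text the test case is covered. Steps 2 and 3 cannot both describe what happens.
4. Table 5 counts possibly, probably and definitely as related, so the test case is a serious adverse reaction under Table 4. Whether it is then expected depends on which section is read.
5. The waiver falls on the wrong events. Under 11.5.2, expectedness is assessed for related SAEs. Section 11.4.2 waives expedited reporting because expectedness is already settled. That reason bears on related events, yet these are not set apart.

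**Timing.** Latest time from site awareness to the regulator = limit for site to Trial Office + onward limit in section 11.6.

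- Fatal or life-threatening SUSAR: outcome form 14 + 7 = 21 days; SAE form 1 + 7 = 8 days.
- Other SUSAR: outcome form 14 + 15 = 29 days; SAE form 1 + 15 = 16 days.

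The difference is 14 - 1 = 13 days in each case. The 7 and 15 days run from notification, so the longer totals breach no limit that the protocol states.

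**The case against.** The strongest reply is that other text already covers these events. Section 11.5.2 has the CI review all SAEs, with no exception for the list, and assess every related SAE against Table 6. SUSAR status is tied to the RSI, not to 11.4.2. Section 11.6 sends all serious adverse reactions to the annual report, and Table 4 defines these by relatedness and seriousness, not by form. Section 10.11 is triggered by a judgement of relatedness, not by an SAE CRF. Section 11.4 puts causality in the notes for every SAE, and 11.5.1 applies the same categories to AEs and exempt SAEs in source data. The outcome form is not shown, and Table 8 is expressly not exhaustive, so the form may already ask for causality. Listed events still reach the Trial Office within 2 weeks, section 18.6 supplies safety data to the DMC, and exacerbations are compared by arm as a secondary outcome. Cardiovascular events remain foreseeable here, because section 6.2 excludes only severe angina and unstable disease.

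Much of this stands, and it limits the point. A reader might infer that listed events receive no CI causality review, can never be SUSARs, drop out of the annual report and never prompt the section 10.11 review. The documents do not support that, because the text just cited says otherwise.

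A reader might also try to count deaths that escape review from the 3% in section 15.1. That figure is a loss to follow-up allowance based on mortality data. It says nothing about relatedness, and the protocol gives no cause-of-death split. Nor does the contradiction show that every death needs the 24-hour route: a SUSAR must be related and unexpected, and death alone makes it neither.

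The reply does not remove the conflict. Causality in the notes is at the site, not at the Trial Office. Section 10.11 needs a prior finding of relatedness. The line on reviewing all SAEs does not say how an event on the outcome form reaches the CI, or that this review covers causality.

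**Conclusion.** The point holds as an unreconciled contradiction in the safety reporting rules. Sections 11.4.2 and 11.4.3 conflict with section 11.5.2 and Table 4 on what decides expectedness, and they leave the four listed classes without a stated route to form-based PI causality grading and independent CI review. A site could comply fully with 11.4.2 while a related listed event missed CI causality review and SUSAR classification. If such an event were picked up, it could arrive up to 14 days after site awareness instead of 24 hours.

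The number of events affected cannot be derived from the protocol. It depends on how many listed events are related, on whether the RSI defines them, and on what the outcome form records, none of which is given. The timing figures assume that each stated limit is used in full and that the onward clock starts when the Trial Office receives the form.

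The passages need to be reconciled because they concern reporting of serious reactions in a trial of a medicinal product, and because the correction is cheap.

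**What to change.** Reconcile sections 11.4.2 and 11.4.3 with section 11.5.2 and Table 4:

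1. State that the RSI alone decides expectedness for SUSAR purposes. Remove the wording in 11.4.2 that makes the list an expectedness rule.
2. State that the list only sets reporting speed, and only for events the PI has assessed as unrelated. These keep the 2-week route.
3. Make sure that the form used for listed events carries the PI's causality assessment to the Trial Office. If the outcome form already has this field, say so in the protocol.
4. Send any listed event judged possibly, probably or definitely related through the SAE CRF and CI review.

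The cost is protocol wording, a causality field if the form lacks one, and a small number of extra expedited forms. No visits are added.
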